7.4.2.5 Time to Initiation of a New Antineoplastic Therapy

Time to initiation of a new antineoplastic therapy will be analyzed using the same analysis methods as for primary analysis of TPP.

7.4.2.6 PSA Undetectable Rate

The PSA undetectable rate (also referred as the rate of PSA decline to <0.2 ng/mL) is defined as the percentage of patients with detectable (≥ 0.2 ng/mL) PSA at baseline, which becomes undetectable (< 0.2 ng/mL) during study drug.

In patients of the ITT population with detectable PSA at baseline, the PSA undetectable rates in enzalutamide+ADT and placebo+ADT will be compared by use of the stratified Cochran-Mantel-Haenszel score test.

The SAS code used to implement the Cochran-Mantel-Haenszel score test will be the same as PSA Response $\geq 50\%$ and PSA Response $\geq 90\%$ in Section 7.4.2.4.

In addition to providing the planned 95% CI for PSA undetectable rate (using the Clopper-Pearson method based on the exact binomial distribution), the difference in response rates between the treatment groups was summarized along with the 95% CI based on the asymptotic distribution.

7.4.2.7 Objective Response Rate and Tumor Response

The ORR is calculated as the percentage of patients of the ITT population with measurable disease at baseline who achieved a complete or partial response in their soft tissue disease using the RECIST version 1.1 criteria; that is with CR or PR as best RECIST overall response.

The stratified Cochran-Mantel-Haenszel score test will be used to compare enzalutamide+ADT versus placebo+ADT.

The SAS code used to implement the Cochran-Mantel-Haenszel score test is similar as described in Section 7.4.2.4.

On patients of the ITT population with measurable disease at baseline, descriptive statistics will be provided, based on investigator assessments, for:

- the best RECIST overall response,
- the ORR

On the ITT population, descriptive statistics will be provided, based on investigator assessments, for:

- the best overall response

- the percentage of patients who achieved a complete or partial response as best overall response
- the RECIST overall time point response, along with the bone lesion response, the overall time point response by visit

The target lesion description, non-target lesion description, new lesions description will be listed by visit. The target lesion response, non-target lesion response, unequivocal new lesions presence along with the overall RECIST time point response derived from investigator assessments, bone lesion response, and the overall time point response as assessed by the investigator will be listed by visit. The best RECIST overall response will be marked in the listing as well. The best overall response will also be listed for investigator assessments.

The number and percentage of CR, PR and non-responders as assessed by the investigator will be included.

In addition to providing the planned 95% CI for ORR (using the Clopper-Pearson method based on the exact binomial distribution), the difference in response rates between the treatment groups was summarized along with the 95% CI based on the asymptotic distribution.

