# **6 DISCONTINUATION**

## **6.1 Discontinuation of Individual Subject(s) From Study Treatment**

A discontinuation is a subject who enrolled in the study and for whom study treatment is permanently discontinued for any reason.

The subject is free to withdraw from the study treatment and/or study for any reason and at any time without giving reason for doing so and without penalty or prejudice. The investigator is also free to terminate a subject's involvement in the study at any time if the subject's clinical condition warrants it.

If a subject is discontinued from the study with an ongoing AE or an unresolved laboratory result that is significantly outside of the reference range, the investigator will attempt to provide follow-up until the condition stabilizes or no longer is clinically significant.

Subject will be discontinued from the study drug treatment if any of the following occur:

- Any AE that is intolerable to the subject which cannot be ameliorated by the use of adequate medical intervention and/or dose reduction or that in the opinion of the investigator would lead to undue risk to the subject if dosing is continued.
- Subject who experiences a seizure or any condition that significantly predisposes the subject to seizure such as brain metastasis or clinically evident stroke.
- Subject who experiences a confirmed event of PRES by brain imaging, preferably by MRI.

- CONFIDENTIAL -

- Subject initiates an investigational agent or new therapy for prostate cancer.
- Subject who has evidence of radiological disease progression as confirmed and in the judgment of the investigator is no longer deriving clinical benefit.
- Subject has discontinued ADT (LHRH agonist/antagonist) and has a testosterone value in the noncastrate range ( $> 50$  ng/dL).
- Dose interruptions  $> 14$  consecutive days. Dose interruptions for subjects who are deriving clinical benefit from treatment may be extended beyond 14 days after sponsor's approval. Dose interruptions of study drug  $\leq 14$  days consecutive are permitted at any point during treatment.
- Subject who is, in the opinion of the investigator or the Medical Monitor, noncompliant with the protocol requirements.
- Subject is lost to follow-up despite reasonable efforts by the investigator to locate the subject.
- Subject withdraws consent for the study.

Subject will be discontinued from the study follow-up (Safety or Long-term Follow-up) if any of the following occur:

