**ORR:**

The ORR is defined as the percentage of subjects with measurable disease at baseline who achieved a complete or partial response in their soft tissue disease using the RECIST version 1.1 criteria on CT/MRI, and for bone lesions on bone scans. Only subjects with detectable lesions will be included in this analysis.

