6.1.2.7 Overall Objective Response Assessment

The overall response assessment is based on RECIST version 1.1 for soft tissue lesion on CT/MRI, and for bone lesions on bone scans. The overall objective response is based on RECIST version 1.1 for soft tissue lesions.

The following categories were used:

- CR = complete response
- PR = partial response (option only for target lesions and overall)
- SD = stable disease (option only for target lesions and overall)
- PD = progressive disease
- Non CR/non PD= not complete response and not progressive disease (not an option for target lesions)
(option only for non-target lesions, bone lesions, and overall)
- Unconfirmed PD (not an option in RECIST on soft tissue lesions)
- NE = not evaluable (option for bone lesions)
= not evaluated/ not all evaluated (option for target and non target lesions)
= inevaluable (option for overall)
- NA = not applicable (postbaseline assessment in case of no lesion of the kind at baseline)
(not an option for overall response assessed by Investigator)

At each time point, the RECIST overall time point response, in patients with measurable soft tissue lesions at study entry (all patients, who have at least one target lesion), can be derived according to RECIST for all possible combinations of tumor response assessments in target and non-target lesions in soft tissues with or without the appearance of new unequivocal lesions. RECIST overall time point response derivation is described in Table 4. The RECIST overall time point response will be derived from the assessments provided by the investigators.

Investigator additionally considers image quality to perform their assessments.

For patients with no target and no non-target soft tissue lesion at baseline, the RECIST overall time point response is set to 'NA', unless an unequivocal new lesion is identified (in which case the assessment is PD) or unless imaging is not evaluable (in which case the assessment is NE).

Table 4 RECIST Overall Time Point Response for all Combinations of Tumor Responses in Target and Non-target Lesions with or without Appearance of new Lesions as assessed by Investigators

Target Lesions*	Non-Target Lesions*	Uequivocal New Lesions^	RECIST Overall Response^
CR	CR	No	CR
CR	Not applicable	No	CR
Not applicable	CR	No	CR
CR	Non-CR/Non-PD	No	PR
CR	Not evaluated	No	PR
PR	Not PD	No	PR
SD	Not PD	No	SD
PD	Any	Yes or No	PD
Any	PD	Yes or No	PD
Any	Any	Yes	PD
Not applicable	Non-CR/Non-PD	No	Non-CR/Non-PD

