Not applicable	Not applicable	No	Not applicable \$
Not applicable	Not evaluated or Not Done	No	NE
Not evaluated or Scan not Done	Not PD	No	NE

* The category “Any” includes all possible categories (incl. NE or NA or Not Done). The category “Not PD” includes: CR, Non-CR/Non-PD, NA, NE and Not Done.

^ Missing assessments during study visits will not be imputed. Missing assessments for “Uequivocal new lesions” will be reported as “Missing” and will lead to “NE” for the derived RECIST Overall Response.

\$ The RECIST overall time point response will only be derived to “Not applicable” for patients with no target and no non-target soft tissue lesions at study entry in absence of new unequivocal lesion.

Definition of Best RECIST Overall Response

In patients with measurable soft tissue lesions at study entry (all patients, who have at least one target lesion), the best RECIST overall response in the soft tissue disease is the best of the RECIST overall time point response assessment reported at any time during or at the end of the treatment period, up to the start of any other antineoplastic prostate cancer therapy. The best RECIST overall response assessment is according to the following decreasing order, starting with the possible best response: CR, PR, SD, Non-CR/Non-PD, PD, NA, NE. For patients still on treatment after or by the cut-off date, the best RECIST overall response can be derived as the best of the RECIST overall time point response assessments recorded for the time on study up to the data cut-off date. Patients with no post-baseline assessment at any visit are reported in the ‘Not evaluated’ category.

The best RECIST overall response will be derived from the assessments provided by the investigators.

Definition of Best Overall Response

At each time point, the overall time point response assessment reported by the investigators are based on the combination of the time point assessments on soft tissue on target lesions, non-

target lesions and apparition of new lesions (i.e. RECIST), and the time point response assessment on bone scan.

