The best overall response is the best of the overall time point response assessment reported at any time during or at the end of the treatment period, up to the start of any other prostate cancer therapy. The best of the overall time point response assessments is according to the following decreasing order, starting with the possible best response: CR, PR, SD, Non-CR/Non-PD, unconfirmed PD, PD, NA (for Investigator only), NE. For patients still on treatment after or by the cut-off date, the best overall response can be derived as the best of the overall time point response assessments recorded for the time on study up to the data cut-off date. Patients with no post-baseline assessment at any visit are reported in the 'Not evaluated' category.

The best overall response will be derived from the overall time point response assessments provided by the investigators.

Table 5 describes the possible combinations of tumor response to report the overall timepoint response assessment.

Table 5 RECIST Combined Time Point Response Provided for any Combinations of Tumor Responses in Soft tissue Lesions and Bone Lesions

RECIST 1.1	Bone Scan	The Combined (i.e., Overall) Time Point Response	
CR	CR	CR	
CR	NA	CR	
NA	CR	CR	
CR	NON-CR/NON-PD	PR	
CR	PDu	PR	
PR	CR	Not NE = & not PD	PR
PR	NON-CR/NON-PD		PR
PR	PDu		PR
PR	NA		PR
SD	CR	Not NE = & not PD	SD
SD	NON-CR/NON-PD		SD
SD	PDu		SD
SD	NA		SD
PD	Any	PD	
Any	PD	PD	
NON-CR/NON-PD	CR	Not NE = & not PD	NON-CR/NON-PD
NON-CR/NON-PD	NON-CR/NON-PD		NON-CR/NON-PD
NON-CR/NON-PD	PDu		NON-CR/NON-PD
NON-CR/NON-PD	NA		NON-CR/NON-PD
NA	NON-CR/NON-PD	NON-CR/NON-PD	
NA	PDu	PDu	
Any but PD	NE	NE	
NE	Any but PD	NE	
NA	Not applicable	NA	

PDu: unconfirmed Progression of Disease.

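### Best response has no stop at radiographic progression, so a CR or PR first recorded after an rPFS event can count towards ORR

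*SAP*

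**What the plan says.** **Definition of ORR.** The ORR entry in Protocol 7.4.2, like the synopsis, describes a "complete or partial response in their soft tissue disease using the RECIST version 1.1 criteria on CT/MRI, and for bone lesions on bone scans", in subjects with measurable disease at baseline. It gives no rule for combining the soft-tissue and bone findings. SAP 6.1.2.7 states its own reading: "The overall objective response is based on RECIST version 1.1 for soft tissue lesions". SAP 7.4.2.7 then counts responders on that basis ("that is with CR or PR as best RECIST overall response") and compares the arms with the stratified Cochran-Mantel-Haenszel test.

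**Window and ranking.** Under SAP 6.1.2.7 the best RECIST overall response is the best time-point response "reported at any time during or at the end of the treatment period, up to the start of any other antineoplastic prostate cancer therapy". For men still on treatment it runs to the data cut-off. The order from best to worst is "CR, PR, SD, Non-CR/Non-PD, PD, NA, NE". The second variable, best overall response, combines soft tissue and bone through SAP Table 5 ("RECIST Combined Time Point Response Provided for any Combinations of Tumor Responses in Soft tissue Lesions and Bone Lesions"). Its window is also open until other prostate cancer therapy or data cut-off. Neither variable stops at progression.

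**Treatment after progression.** Protocol 6.1, like the synopsis, lists this reason for stopping study drug: "Subject who has evidence of radiological disease progression as confirmed and in the judgment of the investigator is no longer deriving clinical benefit". The note to exclusion criterion 6 in Protocol 12.10.4 likewise foresees men who progressed radiographically in the double-blind period and stayed on treatment under the protocol.

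**The concern.** An objective response rate is normally read as the share of patients whose tumour shrank before the disease got worse. Here the best-response rule looks only at rank, not at order in time. Time points after progression can exist because the Protocol 6.1 criterion joins two conditions: confirmed progression, and loss of clinical benefit. A man who meets only the first can go on having on-treatment scans every 12 weeks.

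If his first CR or PR falls at one of those later scans, he is an rPFS event in one table and an ORR responder in the next. At stake is what ORR means and whether it agrees with rPFS. A longer window can only add responders, never remove them, so the rate in either arm can only be too high relative to a rule that stops at progression.

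**Working it through.** The documents give no planned ORR, no number with measurable disease and no ORR power, so there is no figure to reproduce. The check applies the written rules to example visit sequences.

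**Inputs.**
- Best-response windows and rankings, and Table 5: SAP 6.1.2.7.
- Responder definition: SAP 7.4.2.7.
- Progression: SAP 6.1.2.1, Table 3. Soft-tissue PD at any visit, and at least 2 new bone lesions at week 25 or later, need no confirmatory scan.

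Table 5 makes a time point PD if either component is PD. SD or PR in soft tissue with Non-CR/Non-PD on bone (written N below) stays SD or PR. Entries are soft tissue/bone at weeks 13, 25 and 37. The last two columns use assessments up to and including first progression.

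| Sequence | ORR, SAP rule | Combined CR/PR, SAP rule | ORR, stopped | Combined CR/PR, stopped |
|---|---|---|---|---|
| A: SD/N, PR/PD, PR/PD | yes | no | yes | no |
| B: SD/N, SD/PD, PR/N | yes | yes | no | no |
| C: PD/N, PR/N | yes | yes | no | no |
| D: PR/N, PR/PD | yes | yes | yes | yes |

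- **B and C are the problem cases.** The rPFS event comes first (week 25 in B, week 13 in C) and the first PR comes at the next scan. The SAP rule counts both men as responders, on the tested ORR and on the combined variable.
- **D is a valid response.** It precedes progression and counts under every rule.
- **A is different.** The soft-tissue PR is first seen at the same visit as bone progression. It stays a soft-tissue response after the change, because that visit is included. Only the combined variable treats it as non-response.

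Moving to the combined variable without a stop would change A but leave B and C as responders. The stop is therefore needed on both variables.

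**Size per patient.** The measurable share is an assumption, taken as 30-60% of 180.
- 0.30 × 180 = 54, which at 2:1 is 36 enzalutamide and 18 placebo.
- 0.60 × 180 = 108, which is 72 and 36.
- One reclassified patient on enzalutamide: 1/72 = 1.4 points to 1/36 = 2.8 points.
- One reclassified patient on placebo: 1/36 = 2.8 points to 1/18 = 5.6 points.

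These figures show sensitivity to one patient. They do not estimate how many patients are affected.

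**The case against.** **The path is exceptional.** It needs progression, continued study drug, no new therapy, and a first CR or PR at a later scan. The general rule in Protocol 5.1.1 and 5.3.1.2 is treatment until progression. SAP 7.4 confines efficacy to the double-blind period, and under Protocol 12.10.2 open-label scan data are not collected. Protocol 5.3.1.2 also asks for an overall best response at the end of each subject's study, with no stop at progression. This stands as an argument about frequency. It does not change what the SAP rule does when such a case occurs.

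**Little rests on ORR.** SAP 7.1 says p-values outside the primary endpoint are to be read descriptively. That also stands.

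Four stronger readings are tempting, and the documents do not support them:

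- *The SAP tests the wrong endpoint by leaving out bone.* The protocol sentence places the response in soft tissue, requires measurable disease, and then adds bone scans without a combination rule. Its bone-scan criteria (Protocol 5.3.1.2, Table 2) define progression, not response. The SAP states its soft-tissue reading openly, and Table 5 exists only in the SAP. SAP 7.4.2.7 still summarises the combined response, though on the whole ITT population. The wording needs reconciling, but this does not show that the tested endpoint is wrong.
- *Any man whose bone disease progressed is wrongly counted.* Sequence D shows otherwise.
- *Table 5 is in error because soft-tissue PR with unconfirmed bone progression scores as PR and is not reset on confirmation.* A reset presumes that confirmed week-13 bone progression is dated to week 13. SAP 6.1.2.1 refers to first objective evidence but gives no explicit dating rule for this case, and the time-point responses are those reported by investigators.
- *The comparison favours one arm.* Nothing in the documents shows a difference between arms in post-progression responses.

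**Conclusion.** The concern holds for responses first recorded after progression. As written, SAP 6.1.2.7 can count a first CR or PR after a soft-tissue or bone rPFS event as an objective response, both in the tested ORR and in the combined best overall response. Responses before progression are unaffected.

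The direction is certain: either arm's rate can only be raised. The number affected cannot be computed, because the documents give neither the number with measurable disease nor the frequency of continued treatment with a later first response. It is probably small. The per-patient figures rest wholly on the assumed 30-60% measurable share. The TTPP conclusion and its type I error are not touched.

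The bone-scan wording is a separate, lesser matter: an ambiguous protocol sentence and a narrower but stated SAP reading, to be reconciled in writing. This is an analysis point only and implies nothing about when treatment should stop.

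**What to change.** 1. **SAP 6.1.2.7 and 7.4.2.7.** For both best RECIST overall response and best overall response, use only time-point assessments up to and including the first radiographic progression by the rPFS definition, or up to the start of new therapy or data cut-off if earlier. Take the progression date from the rPFS derivation, and state there how a confirmed week-13 bone progression is dated, so that the two endpoints agree.
2. **ORR wording.** Say explicitly how the protocol phrase "using the RECIST version 1.1 criteria on CT/MRI, and for bone lesions on bone scans" is applied. Keep the soft-tissue ORR as the tested rate. Add the combined (Table 5) CR/PR rate in the same measurable-disease subset as a supportive analysis. Note beside it that Table 5 turns a soft-tissue CR or PR into NE when that visit's bone scan is not evaluable, so the combined rate can be lower for reasons other than progression.

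**Cost.** This needs SAP text and a re-derivation from investigator assessments already collected and listed. SAP section 1 allows revision before database hard lock. The reported ORR may be slightly lower in either arm.

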7.4.3 Analysis of Exploratory Efficacy Endpoints

7.4.3.1 Quality of Life

BPI-SF average score will be summarized descriptively by visit, by presenting the mean, standard deviation, minimum, maximum and median of the results and change from baseline. A listing of all items scores will be provided.

The 5 FACT-P subscales (Physical, Social/Family, Emotional, Functional, Prostate Cancer Subscale) and the total FACT-P will be summarized descriptively by visit, by presenting the mean, standard deviation, minimum, maximum and median of the results and change from baseline. A listing of all items scores will be provided along with a listing of the EQ-5D-5L will be provided as well.

The QLQ-PR25 questionnaire will be summarized by descriptive statistics after scoring their scales and items. QLQ-PR25 will also be analyzed on the subgroup of patients who reached the 1 year time point.

The QLQ-PR25 is composed of both multi-item scales and single-item measures as follows:

- ➔ Urinary symptoms and problems (8 items: Q31 – Q37, Q39)
- ➔ Incontinence aids (Q38)
- ➔ Bowel symptoms/function (4 items: Q40 – Q43)
- ➔ Treatment-related symptoms (6 items: Q44 – Q49)
- ➔ Sexual activity (2 items: Q50, Q51)
- ➔ Sexual functioning (4 items: Q52 – Q55)

In order to score a (sub)scale, first the raw score (RS) is computed by averaging the raw values of the individual items that contribute to the (sub)scale and then the RS is linearly transformed using the range of item raw values so that scores range from 0 to 100. Specifically, the scores of these scales and the individual items will be calculated based on

$[(RS-1)/range] \times 100$. However, for Q53 to Q55, before scoring the raw value of an individual item will be subtracted from 5 (i.e., 5 – raw value).

For handling missing items, if half or more questions within scale are answered then a score will be calculated for that scale. Otherwise the patient score for that scale will be missing. A high scale score represents a higher response level. The scale scores and change from baseline will be summarized by descriptive statistics by visit. A listing of all items scores and a (sub)scale scores will be provided.

Time to Deterioration of QoL

Time to deterioration of QoL will be analyzed using the same analysis methods as for primary analysis of TPP.

7.4.3.2 Time to Pain Progression

Time to pain progression will be analyzed using the same analysis methods as for primary analysis of TPP.

7.4.4 Analysis of Other Efficacy Variables

Not applicable.

7.5 Analysis of Safety

All analysis of safety will be presented by treatment group for SAF, unless specified otherwise. All AEs will be listed.

